The laboratory tests listed in [Table 2](#) will be performed by the central laboratory service provider at Visits 1, 2, 4, 6, 8, 10, 12, 16, 20, EOT and at Week 188 follow-up visit ("complete" lab). At Visits 3, 5, 7, 9, 11, 13, 14, 15, 17, 18, 19, 21, only WBC, serum CRP and serum albumin will be collected ("targeted" lab). A local laboratory may be used for selected tests in exceptional cases. Subjects should be fasting for at least 8 hours prior to the blood sample being taken at the "complete" visits, except for screening (see [Appendix C](#)).

Instructions regarding sample collection, sample handling/processing and sample shipping are provided in the Laboratory Manual in the ISF. For time points of laboratory sampling, see [Appendix C](#).

Laboratory results (i.e., all safety laboratory and clinical laboratory data relevant for current clinical practice) of the subjects will be available in real time to the respective investigator (via laboratory reports) and to the sponsor (via the central laboratory website) and selected abnormal laboratory alerts will be flagged to the site and sent to sponsor in real time.

A clinically relevant value may be either in or outside the reference range. Clinically relevant abnormal laboratory test results must be confirmed using an unscheduled visit laboratory kit and should be repeated until normalization or stabilization or until an alternative explanation has been found. Laboratory abnormalities are considered to be adverse events only if they result in discontinuation from the study, necessitate therapeutic medical intervention, and/or if the investigator considers them to be adverse events.

Table 2. Laboratory Tests

Category	Test Name
Hematology	Hematocrit (Hct) Hemoglobin (Hb) Red Blood Cell Count/Erythrocytes White Blood Cells/Leukocytes Platelet Count/Thrombocytes
Diff. Automatic	Neutrophils (relative count) Eosinophils (relative count) Basophils (relative count) Monocytes (relative count) Lymphocytes (relative count)
Diff. Manual (if Diff Automatic is abnormal)	Neutrophils, bands (Stabs) Neutrophils, polymorphonuclear (PMN) Eosinophils Basophils Monocytes Lymphocytes
Enzymes	AST(GOT) ALT(GPT) Alkaline Phosphatase (AP) Creatine Kinase (CK) CK-MB, only if CK is elevated Gamma-Glutamyl Transferase (GGT/γ-GT)
Electrolytes	Calcium Sodium Potassium Chloride Bicarbonate

Table 2. Laboratory Tests (Continued)

Category	Test Name

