Substrates	Glucose BUN Creatinine eGFR (estimated by CKD-EPI formula) Bilirubin Total Bilirubin Direct (if total is elevated) Bilirubin Indirect (if total is elevated) Albumin C-Reactive Protein (CRP) (high sensitivity) Cholesterol, total Triglycerides LDL-Cholesterol HDL-Cholesterol
Urine Pregnancy test (only for female subjects of childbearing potential) ^d	Human Chorionic Gonadotropin in the urine
Serum Pregnancy test (in all female subjects at screening or if urine pregnancy test is positive)	Human Serum Chorionic Gonadotropin
Autoantibodies (only at screening)	Rheumatoid Factor
Urinalysis (dipstick)	Urine Nitrite Urine Protein Urine Glucose Urine Ketone Urobilinogen Urine Bilirubin Urine RBC/Erythrocytes Urine WBC/Leukocytes Urine pH Urine creatinine
Urine-Sediment (microscopic examination, only if urine analysis abnormal)	Urine Sediment Bacteria Urine Cast in Sediment Urine Squamous Epithelial Cells Urine Sed. Crys., Unspecified Urine Sediment RBC/Erythrocytes Urine Sediment WBC/Leucocytes
Urine	Albumin (quantitative)

Table 2. Laboratory Tests (Continued)

Category	Test Name
Infection screening	Hepatitis B Surface Antigen (qualitative) ^a Hepatitis B Surface Antibody (qualitative) ^a Hepatitis B Core Antibodies total (qualitative) ^a Hepatitis B Virus DNA (quantitative) ^{a,b} Hepatitis C Antibodies (qualitative) ^a Hepatitis C Virus RNA (quantitative) ^a HIV-1, and HIV-2 Antibody (qualitative) ^a PPD or QuantiFERON [®] -TB ^c

- a. Hepatitis B, Hepatitis C and HIV testing will be performed at screening.
- b. If Hepatitis B Surface Antigen is negative but Hepatitis B Core Antibodies total is positive and/or Hepatitis B Surface Antibody is positive, Hepatitis B Virus DNA will be quantified. If Hepatitis B Virus DNA level is undetectable at screening, the subject can participate in this trial. In these cases, HBV DNA level will be monitored at least every 6 months. If positive, the subject's treatment will be discontinued. If Hepatitis C Virus Antibodies is positive, Hepatitis C Virus RNA will be quantified. If Hepatitis C RNA level is undetectable at screening, the subject can participate in this trial. In these cases, HCV RNA level will be monitored at least every 6 months. If positive, the subject's treatment will be discontinued.
- c. TB testing will be performed at screening, Visit 12, 16, 20 and Week 184.
- d. Urine pregnancy test will be performed at all dosing visits.

Other Safety Parameters

Local Tolerability

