5.3.4 Safety Variables

Safety will be assessed descriptively based on:

- Adverse events (AE)
- Serious adverse events (SAE)
- Clinical laboratory values (hematology, clinical chemistry and urinalysis)
- Vital signs
- Local tolerability

Major Cardiac, Cerebrovascular and Thrombotic Events Adjudication Committee

An independent adjudication committee will be used to adjudicate all observed cardio- and cerebro-vascular events reported during the conduct of the study to assure consistent assessment of major cardiac, cerebrovascular and thrombotic events. The events that are adjudicated and the adjudication process will be detailed in the CCVT Adjudication Committee Charter. Site personnel will collect source documentation for the identified events and submit to the CCVT Adjudication Committee. Source documentation should be obscured before submission by site personnel.

Source documentation: (below types of source may be included with the case and will vary depending on type of event and available source):

- SAE form or narrative
- Hospital Discharge Summary

- Death Summary/Details of death note
- Local Lab Values (e.g., normal ranges; cardiac biomarkers)
- Imaging reports (e.g., X-Ray, CT, MRI, MRA, Angiography, Ultrasonography)
- Consultation Notes (e.g., Cardiology, Neurology)
- Procedure Reports (e.g., cardiac catheterization, PCI, CABG)
- Echocardiography
- Admission History/Emergency Room report
- Autopsy result
- Death Certificate
- Clinical Course (e.g., progress notes, doctor visit notes)
- Narrative Form
- ECG
- Other Source (specified)

Details to perform the assessments and complete the necessary documentation will be available in the adjudication charter and investigator training material.

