5.6.2 Appropriateness of Measurements

All measurements performed during this trial are standard measurements in GPP and/or EP treatment trials and will be performed in order to monitor safety aspects or assess treatment response in an appropriate way. Therefore, the appropriateness of all measurements applied in this trial is given.

5.6.3**Suitability of Subject Population**

The subjects enrolled in the present study are subjects with GPP or EP, in agreement with the indication that is being pursued.

The inclusion and exclusion criteria, for most of them limit the factors of variability that could confuse efficacy and safety outcomes and/or have the purpose of protecting subject's safety.

Any active ongoing inflammatory disease other than GPP or EP that might confound efficacy evaluation according to investigator's judgment is exclusionary, as well as the intake of psoriasis medications that may interfere with risankizumab in the evaluation of the psoriatic disease.

GPP is a potentially severe disease and EP may lead to dehydration. Both diseases may be fatal. In order to protect subject's safety and control, medical conditions that could, in the opinion of the investigator, compromise the safety of the subjects are exclusionary. This is also the case for the exclusion criteria relating to GPP and EP.

Moreover, the restriction of the subject population will facilitate the interpretation of safety results.

5.6.4**Selection of Doses in the Study**

A dose of 150 mg has been selected for global Phase 3 trials of risankizumab for psoriasis. The dose selection strategy for global Phase 3 involved analyses of data from the completed Phase 1 study (Trial 1311.1, c02434648), the Phase 2 study (Trial 1311.2, c03272682) and PK-Pharmacodynamic analysis of all available data from the Phase 1 and 2 studies. In Study 1311.16, following single dose administration of risankizumab 18 mg to 300 mg SC doses. [REDACTED]

[REDACTED]

[REDACTED]

[REDACTED] in the

Phase 2 study (Trial 1311.2). Therefore, the dose of 150 mg was selected in this trial, which is the same dose as being evaluated in other global Phase 3 trials of risankizumab for psoriasis.

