8.1.6 Safety Analyses

Adverse events will be coded using the Medical Dictionary for Regulatory Activities (MedDRA[®]) coding dictionary. Standard AbbVie summary tables and listings will be produced.

All AEs, SAEs, AEs leading to discontinuation, and pre-specified AEs of special interest will be collected during the study. A treatment-emergent AE (TEAE) is defined as an event with onset or worsening after the first study dose of risankizumab and within 15 weeks (105 days) after the last risankizumab injection. The number and percentages of subjects experiencing TEAE will be tabulated using the MedDRA system organ class and preferred term. Summaries (including percentages and event per 100 subject-years) of SAEs, deaths, AEs leading to discontinuation from the study, and pre-specified AEs of special interest will be provided as well. Mean change in laboratory variables, and vital signs determinations will be summarized. For selected parameters, a listing of all subjects with clinically significant laboratory values and vital sign determinations will be

provided. Shift tables for changes from baseline according to the normal range will also be provided.

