11.3.2 Statistical Methods

Analysis of Quantitative Laboratory Parameters (Hematology, Chemistry and Urinalysis)

Though the protocol indicates utilizing the Rheumatology Common Toxicity Criteria (RCTC) scale for grading laboratory values, given that the National Cancer Institute Common Toxicity Criteria for Adverse Events (NCI CTCAE) scale includes a more comprehensive list of laboratory values, the lab analyses based on the NCI CTCAE scale will be presented. Changes from Baseline to each scheduled visit and to the final value in continuous laboratory parameters will be summarized with the mean, standard deviation and median.

If there are multiple post-baseline measurements on the same day, average value will be used.

Shift Tables

Shift tables for changes from Baseline according to the normal range will be provided for each hematology, clinical chemistry and urinalysis (pH only) parameter. Shifts from Baseline to the following endpoints will be considered: minimum value, maximum value and final value. Categories of "low or normal" and "high or normal" will be included at Baseline in addition to the categories of "low," "normal," "high" and "missing." If there are multiple post-baseline measurements on the same day, last value will be used.

Potentially Clinically Significant Laboratory Values

Frequencies and percentages of subjects with post Baseline lab values met the following criteria in [Table 65](#) and [Table 76](#) will be summarized.

Table 65. Criteria for Potentially Clinically Important Chemistry Values

Chemistry Variables	Units	Definition of Potentially Clinically Important Current (Version 4) NCI CTCAE Grade 3 or Greater	
		Very Low	Very High
TBL	mcmol/L		> 3.0 × ULN
ALP	U/L		> 5.0 × ULN
SGOT/AST	U/L		> 5.0 × ULN
SGPT/ALT	U/L		> 5.0 × ULN
Albumin	g/L	< 20	
Glucose	mmol/L	< 2.2	> 13.9
Triglycerides	mmol/L		> 5.7
Creatinine	mcmol/L		> 3.0 × ULN
Sodium	mmol/L	< 130	> 155
Potassium	mmol/L	< 3.0	> 6.0
Calcium	mmol/L	< 1.75	> 3.1
CPK	U/L		> 5.0 × ULN
Total Cholesterol	mmol/L		> 10.34
GGT			> 5.0 × ULN

Table 76. Criteria for Potentially Clinically Important Hematology Values

Hematology Variables	Units	Definition of Potentially Clinically Important Current (Version 4) Grade 3 or Greater	
		Very Low	
Hemoglobin	g/dL	< 8.0	
Platelets count	10 ⁹ /L	< 50.0	
WBC count	10 ⁹ /L	< 2.0	
Neutrophils	10 ⁹ /L	< 1.0	
Lymphocytes	10 ⁹ /L	< 0.5	

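### The SAP narrows urinalysis to pH, so urine abnormalities not reported as adverse events enter no specified laboratory shift or abnormality table

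*Protocol*

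**What the plan says.** **Protocol.** Table 2 (Section 5.3.1.1) lists under dipstick urinalysis "Urine Nitrite Urine Protein Urine Glucose Urine Ketone Urobilinogen Urine Bilirubin Urine RBC/Erythrocytes Urine WBC/Leukocytes Urine pH Urine creatinine". A separate urine row holds quantitative albumin. Sediment is also examined, but conditionally ("microscopic examination, only if urine analysis abnormal"). The Table 2 tests are done "at Visits 1, 2, 4, 6, 8, 10, 12, 16, 20, EOT and at Week 188 follow-up visit". Section 5.3.4 counts urinalysis among the safety variables ("Clinical laboratory values (hematology, clinical chemistry and urinalysis") without limiting it to pH. Section 8.1.6 promises mean changes in laboratory variables and adds: "Shift tables for changes from baseline according to the normal range will also be provided".

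**SAP.** The laboratory test table in 11.3.1 (printed as Table 54) has one urine entry, pH. In 11.3.2, shift tables are to be "provided for each hematology, clinical chemistry and urinalysis (pH only) parameter". The two tables of potentially clinically important values cover chemistry and haematology only. Two general sentences name no analytes: 11.3 promises listings and descriptive statistics of laboratory values, and 11.3.2 promises changes from baseline in continuous laboratory parameters, under a heading that includes urinalysis. Section 14.0, on changes from the protocol, is marked as not applicable.

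**The concern.** Safety is a primary objective (Protocol 4.0), treatment runs to 172 weeks, and the trial is meant to support registration (Protocol 3.0). The protocol names urinalysis as a class and promises laboratory shift tables. The SAP keeps one item from that class and does not say why.

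Shift tables matter because they do not depend on anyone deciding that a result is an adverse event. Under Protocol 5.3.1.1 a laboratory abnormality becomes an adverse event only if it leads to discontinuation, needs therapeutic intervention, or is judged to be one by the investigator. In this open-label trial that judgement is made knowing the dose. New protein, glucose or blood in the urine, or rising urine albumin, that falls short of those conditions would have no specified shift or abnormality table.

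**Working it through.** There is no sample-size or power figure to reproduce. The check sets the two test lists side by side and counts.

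1. **Routine urine analytes collected (Protocol Table 2).** Dipstick: nitrite, protein, glucose, ketone, urobilinogen, bilirubin, RBC, WBC, pH, creatinine = 10. Quantitative urine albumin = 1. Total 10 + 1 = 11.

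2. **Urine analytes in the SAP test list.** pH = 1. The albumin entry in the SAP sits in the substrates row, as in the protocol, and is the blood test.

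3. **Dropped.** 11 − 1 = 10 of 11 routine analytes. With the 6 conditional sediment tests, 17 − 1 = 16 of 17.

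4. **Is this general shortening of the list?** No. The SAP carries over all 5 haematology, 5 automatic-differential, 5 unconditional enzyme, 5 electrolyte and 13 substrate entries (5 + 5 + 5 + 5 + 13 = 33). From those blood categories it omits only CK-MB and the manual differential, both done only if another result is abnormal. The loss of routine analytes is confined to urine.

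5. **Is it declared?** SAP 11.3.2 explains a different departure, grading laboratory values by NCI CTCAE instead of RCTC. It gives no reason for the pH restriction, and 14.0 records nothing.

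6. **Which outputs are affected?**
   - Shift tables: all urine items except pH are excluded by the wording.
   - Potentially clinically important values: no urine criterion.
   - Mean change: ambiguous for numeric urine albumin. The sentence on continuous parameters could include it, while the test list points to pH alone. Dipstick items reported as categories cannot enter a mean-change table on either reading.
   - Adverse-event tables: an abnormality reported as an adverse event is counted by system organ class and preferred term (SAP 11.2.1).

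7. **How many panels?** Protocol 5.3.1.1 gives post-baseline complete panels at Visits 4, 6, 8, 10, 12, 16, 20, EOT and Week 188, which is 9. SAP Table 2 (Section 6.0) has post-baseline windows at Weeks 8, 16, 28, 40, 52, 100, 148, 172, 184 and 188, which is 10; the extra one is Week 184. With 16 subjects and no dropout: 9 × 16 = 144, or 10 × 16 = 160.

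**The case against.** A reader might infer that new proteinuria, haematuria, glycosuria or albuminuria enters no summary at all and would go unseen. The documents do not support that. Events meeting the adverse-event conditions are tabulated. Results reach investigator and sponsor in real time, selected abnormal values are flagged, and clinically relevant ones must be confirmed and followed (Protocol 5.3.1.1). Serum creatinine, BUN and eGFR stay in the SAP list and its shift tables, and creatinine also has a clinical-importance criterion. The general wording in SAP 11.3 may bring urine data into listings. These points stand, and they limit the finding to aggregate reporting.

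A renal argument from the protocol's remark that "EP may lead to dehydration" (Section 5.6.3) should not be pressed either. The remark describes the disease and supports the exclusion criteria; it is not a drug signal. The SAP's areas of safety interest include no renal category.

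It can also be said that Protocol 8.1 leaves specific details to the SAP, that 8.1.6 does not name every analyte, that graded dipstick results do not fit low/normal/high categories, and that tables with about four subjects per arm in each substudy will be sparse. This is fair as far as it goes. It explains why dipstick items need a different table format, but not why numeric urine albumin is missing or why the restriction carries no rationale. The 10-of-11 count also gives every analyte equal weight, so it measures coverage rather than clinical importance.

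**Conclusion.** The mismatch is in the text of both documents. The protocol collects 11 routine urine analytes and treats urinalysis as a safety variable; the SAP specifies shift tables for one of them and no urine abnormality criterion, without a stated reason. Urine abnormalities not reported as adverse events therefore enter no specified laboratory shift or abnormality table. For quantitative urine albumin, inclusion in the mean-change summaries is ambiguous; exclusion is not established.

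The size is 10 of 11 routine analytes over 144 scheduled post-baseline panels by the protocol's visit list, or 160 if the SAP's Week 184 window counts. Both figures assume 16 subjects and no dropout. No efficacy result or error rate is affected. It is a modest gap in safety reporting that should be closed because the data are already collected.

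**What to change.** In the SAP laboratory test list (11.3.1) and in 11.3.2:

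- Add quantitative urine albumin to the change-from-baseline summaries and the normal-range shift tables. Add an albumin/creatinine ratio only if urine creatinine is reported as a number; the protocol places it in the dipstick row and does not say.
- Add categorical shifts from baseline to worst post-baseline result for the main dipstick items: protein, glucose, RBC and WBC.
- Record in SAP 14.1 any urine item still left out, with the reason.
- State whether Week 184 is a complete-laboratory visit, so that the protocol text and the SAP windows agree.

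No new data are needed. The cost is SAP wording and a few extra tables, which will be sparse in a 16-subject trial.

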5.3.2 Drug Concentration Measurements

5.3.2.1 Collection of Samples for Analysis

Blood Samples for Risankizumab Assay

Blood samples, approximately 3 mL, for risankizumab assay will be collected at the study visits at the time points specified in [Appendix C](#) by venipuncture into appropriately labeled collection tubes. The timing of blood collection will take priority over all other

scheduled study activities except for ECG, vital signs, and dosing. Blood samples for the PK assay should be collected as closely as possible relative to the time of dosing and within 60 minutes prior to dosing. Date and exact time (to the nearest minute) of drug administration will be recorded on eCRFs.

Eleven samples will be collected per subject for pharmacokinetic analysis during the treatment and follow-up periods.

Blood Samples for Risankizumab Anti-Drug Antibody (ADA) Assay:

Blood samples, approximately 3 mL, for risankizumab ADA assay will be collected at the study visits at the time points specified in [Appendix C](#). Blood samples for the ADA assay should be collected as closely as possible relative to the time of dosing and within 60 minutes prior to dosing. Date and exact time (to the nearest minute) of drug administration will be recorded on eCRFs.

Eleven samples will be collected per subject for ADA analysis during the treatment and follow-up periods.

After completion of the study, PK and ADA plasma samples may be used for further methodological investigations, e.g., stability testing.

5.3.2.2 Handling/Processing of Samples

Details for the handling and processing of the samples will be provided outside this protocol, in the laboratory manual.

5.3.2.3 Disposition of Samples

The frozen plasma samples for risankizumab and risankizumab ADA assays will be packed and shipped from the study site to the Central Laboratory according to instructions in the central laboratory Lab Manual. An inventory of the samples included will accompany the package.

5.3.2.4 Measurement Methods

Plasma concentrations of risankizumab and relative titers of risankizumab ADA will be determined using validated methods under the supervision of the Bioanalysis department at AbbVie. Any additional analytes may be analyzed using non-validated methods.

Plasma samples collected for risankizumab and risankizumab ADA analysis may be used for future assay development or validation activities.

The presence of ADA to risankizumab will be assessed via a tiered approach using a validated electrochemiluminescence assay (screening, confirmatory, and titration analysis as appropriate). Samples that are confirmed positive may be further characterized in a validated neutralizing antibody (NAb) assay.

5.3.3 Efficacy Variables

Primary Endpoint(s)

For generalized pustular psoriasis:

The primary endpoint for Substudy GPP is the proportion of subjects achieving a GPP Clinical Response, defined as at least "Slightly Improved" in the overall improvement rating from baseline, at Week 16, according to JDA total score ([Appendix D](#)) for GPP.

For erythrodermic psoriasis:

The primary endpoint for Substudy EP is the proportion of subjects achieving an EP Clinical Response, defined as at least "Minimally Improved" in Clinical Global Impression-Global Improvement (CGI-GI) ([Appendix G](#)) for EP at Week 16.

Secondary Efficacy Endpoint(s) in Substudy GPP

- Proportion of subjects achieving a GPP Clinical Response at Week 52
- Proportion of subjects achieving $\geq 90\%$ reduction from baseline Psoriasis Area Severity Index (PASI) score (PASI 90) at Week 16
- Proportion of subjects achieving PASI 90 at Week 52

Secondary Efficacy Endpoint(s) in Substudy EP

- Proportion of subjects achieving an EP Clinical Response at Week 52
- Proportion of subjects achieving PASI 90 at Week 16
- Proportion of subjects achieving PASI 90 at Week 52

Other Efficacy Endpoint(s) in Substudy GPP

The following endpoints will be summarized at each scheduled visit that the respective variable is collected:

- Proportion of subjects achieving a GPP Clinical Response, defined at least "Slightly Improved" in the overall improvement rating from baseline according to JDA total score for GPP.
- Change from baseline in each of the JDA component scores
- Change and Percent change from baseline in JDA score
- Change and Percent change from baseline in PASI
- Change from baseline in BSA
- Proportion of subjects achieving PASI 50/75/90/100 response
- Proportion of subjects achieving Dermatology Life Quality Index (DLQI) of 0/0 or 1
- Change from baseline in DLQI
- Proportion of subjects achieving at least two grades of improvement in Physician's Global Assessment of Generalized Pustular Psoriasis (PGA-GPP).

Other Efficacy Endpoint(s) in Substudy EP

The following endpoints will be summarized at each scheduled visit that the respective variable is collected:

- Proportion of subjects achieving an EP Clinical Response, defined at least "Minimally Improved" in CGI-GI for EP
- Proportion of subjects achieving at least "Much Improved" in CGI-GI for EP

- Percent change from baseline in PASI
- Change from baseline in PASI
- Proportion of subjects achieving PASI 50/75/90/100 response
- Change from baseline in BSA
- Proportion of subjects achieving DLQI of 0/0 or 1
- Change from baseline in DLQI

